9.1.2 Adverse Events

Adverse events will be recorded as described in section 8, using CTC v4 and surgical complications

9.1.3 Lymphocytic infiltration pre and post treatment

Pre and post treatment tumor specimens will be formalin-fixed and paraffin-embedded on slides and stained with H&E and evaluated by the collaborator pathologist for the presence/absence of lymphocytes within the tumor tissue.

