2.1.2 Correlative Studies

All participants will be required to participate in the collection of blood and tissue sample for banking and future research studies. Up to 60 mL of blood will be collected at each of the following time points: baseline or pre-treatment, after the first cycle of treatment, after the second cycle of treatment and post cystectomy.

We will also collect archival tissue from a newly obtained core or excisional biopsy of a tumor lesion. Newly-obtained is defined as a specimen obtained up to 6 weeks (42 days) prior to initiation of treatment on week 1. Subjects for whom newly-obtained samples cannot be provided (e.g. inaccessible or subject safety concern) may collect tissue from a previously archived specimen. Additionally, archival tissue from the surgical specimen at the time of cystectomy will also be collected.

Laboratory assays will be used to explore our hypothesis that there will be markers of immune activation/biologic response in the tumors of patients treated with pembrolizumab as compared to control untreated tumor samples from similar patients or the same patient (if tissue is available). This will include, but not be limited to, studying signals of anti-cancer

immunological activity by evaluating the frequency of CD4 and CD8 T cells in tumor tissues (pre and post-therapy or untreated and treated cohorts). We will also evaluate tissue for signals of biomarker activity by evaluating surgical specimens for established and not-so-established markers of response to pembrolizumab (e.g. TILs, PD-1 and PD-L1 levels) compared to pre-treatment biopsy samples. Immune monitoring as a component of internal discovery studies will include but not limited to evaluation of CD4 and CD8 T cells in peripheral blood and available tumor samples as previously published[1-4].

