3.2 Secondary Objectives and Hypothesis

3.2.1 Secondary Objectives

- To explore anti-cancer immunological activity by evaluating surgical specimens for evidence of post-treatment lymphocytic infiltration and residual tumor compared to pre-treatment biopsy samples.

- To explore biomarker activity by evaluating surgical specimens and blood samples for established and not-so-established markers of response to pembrolizumab.
- To report the tumor yield and sufficiency of tumor for immunological and biomarker activity
- To examine the interaction of the human microbiome and pathologic response to Pembrolizumab

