9.1.4 Residual tumor

This will be reported as whether there is any residual tumor in the surgical specimen (present /absent) as well as area of the surgical specimen comprised of residual tumor.

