9.1.5 Biomarker activity

Immunological markers include CD4 and CD8 T cells and biomarker activity includes TILs, PD-1 and PD-L1 levels. These will be measured from the biopsy samples and surgical specimens.

9.1.6 Tumor Yield.

The amount of residual tumor available for analysis and the numbers of patients with assessable samples will be recorded.

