9.4 Analysis Plan

TOX events will be reported with a 95% credible interval assuming a non-informative prior of beta (1,1). Specific events will also be summarized. Then all adverse events and surgical complications will be reported overall by grade, attribution, and treatment period (cycle 1, cycle 2, between the end of cycle 2 and actual surgery, 30 days following surgery). Demographic and baseline laboratory results will be summarized using descriptive and graphical statistics. Changes in markers between biopsy and surgical resection will be compared with a paired t-test or non-parametric alternative as indicated for continuous measures, and with McNemar's test for binary or ordinal measures. The numbers of patients with sufficient samples for laboratory analysis will be used to plan the numbers of patients needed for enough evaluable samples future trials. Similarly this experience will guide planning for the numbers and types of markers that can be reasonably assessed from surgical specimens in this patient population after 'window of opportunity' pembrolizumab treatment.

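### Scoring H&E lymphocytic infiltration only as present or absent means section 9.1.3 cannot register an increase in a tumor that already contains lymphocytes

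*Combined protocol and SAP*

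**What the plan says.** The first secondary objective (3.2.1) concerns the immune response to the cancer, to be studied through "evaluating surgical specimens for evidence of post-treatment lymphocytic infiltration and residual tumor compared to pre-treatment biopsy samples". Section 9.1.3 is the only endpoint named for lymphocytic infiltration. Pre- and post-treatment slides are H&E stained and "evaluated by the collaborator pathologist for the presence/absence of lymphocytes within the tumor tissue".

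Related measures appear elsewhere:

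- Section 9.1.4 records residual tumor as "present /absent) as well as area of the surgical specimen comprised of residual tumor".
- Section 9.1.5 adds further markers: "Immunological markers include CD4 and CD8 T cells and biomarker activity includes TILs, PD-1 and PD-L1 levels". On the tissue to be used, the same section says: "These will be measured from the biopsy samples and surgical specimens". No unit or scoring method is given for TILs.
- Section 2.1.2 also describes a planned study of "immunological activity by evaluating the frequency of CD4 and CD8 T cells in tumor tissues (pre and post-therapy or untreated and treated cohorts". Section 4.2.3.2 repeats this.

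For biopsy-to-surgery changes, 9.4 has continuous markers "compared with a paired t-test or non-parametric alternative as indicated for continuous measures". Markers on the other scales are handled "with McNemar's test for binary or ordinal measures". Section 9.1 says the secondary endpoints are to be described and used in designing later studies.

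**The concern.** The objective concerns change in infiltration from biopsy to cystectomy, and the scale in 9.1.3 registers change only across the line between none and some. A tumor that goes from a sparse to a dense infiltrate is present at both times. It is a concordant pair, so it adds nothing to McNemar's test and shows no change in a descriptive table. Only tumors without lymphocytes at baseline can contribute an increase.

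If most baseline biopsies contain some lymphocytes, the H&E result will look flat because of the scale rather than the drug. Since these endpoints are meant to inform later trials, a flat line produced this way could be carried forward as if it were evidence.

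**Working it through.** The plan gives no sample size, power, alpha or effect size for infiltration, so there is no figure of its own to reproduce.

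**Inputs**

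- Maximum pairs: 20 (Sample Size Considerations). Missing or insufficient tissue would lower this, so 15 and 10 are shown as assumptions.
- Test for a binary paired marker: McNemar (9.4).
- Alpha: two-sided 0.05, assumed.
- Share of baseline tumors already positive, *b*: not in the documents; 30% to 90% is shown.
- Changes from present to absent: assumed to be none, which favors the endpoint.

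**Step 1: changes needed.** With all *k* discordant pairs in one direction, the exact two-sided p-value is 2 × 0.5^k.

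- k = 5: 2 × 0.03125 = 0.0625
- k = 6: 2 × 0.015625 = 0.03125

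Six one-way changes are therefore needed. With 20 pairs, at least six tumors must be negative at baseline. Once 15 or more are positive, at most 20 − 15 = 5 can convert and p<0.05 is out of reach.

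**Step 2: best case.** If every negative tumor converts, the number of conversions is Binomial(n, 1 − b). The chance of six or more is:

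| Positive at baseline | 20 pairs | 15 pairs | 10 pairs |
|---|---|---|---|
| 30% | >99% | >99% | 85% |
| 50% | 98% | 85% | 38% |
| 60% | 87% | 60% | 17% |
| 70% | 58% | 28% | 5% |
| 80% | 20% | 6% | 0.6% |
| 90% | 1% | 0.2% | <0.1% |

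**Step 3: incomplete conversion.** If each negative tumor converts with probability *c*, the count is Binomial(n, (1 − b)c). With 20 pairs:

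| Positive at baseline | c = 80% | c = 50% |
|---|---|---|
| 50% | 87% | 38% |
| 60% | 66% | 20% |
| 70% | 34% | 7% |
| 80% | 9% | 1% |

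**Step 4: a continuous measure on the same pairs.** For a two-sided paired t-test at 0.05 with 80% power (noncentral t), the detectable mean change, in standard deviations of the within-patient difference, is about 0.67 with 20 pairs, 0.78 with 15 and 1.00 with 10. The share of tumors positive at baseline does not enter this calculation.

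**The case against.** A reader might infer that the first secondary objective cannot be answered whatever the drug does. The documents do not support that. Sections 2.1.2 and 4.2.3.2 use the objective's own notion of anti-cancer immunological activity and tie it to CD4 and CD8 frequency, which is quantitative. Section 9.1.5 measures those cells and TILs on both biopsy and surgical tissue, and 9.4 supplies a paired continuous test. The objective also covers residual tumor, which is recorded with an area. A sparse-to-dense change could therefore appear in the other measures even if the H&E line stays flat.

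It is also fair to say that p<0.05 is not a criterion the plan sets for this endpoint, and that the endpoint works reasonably well with 20 pairs if about half or fewer of the tumors are positive at baseline and most of the negative ones convert.

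Nor do the documents establish that baseline positivity is high. Section 4.2.1 treats BCG as immunotherapy, but says nothing about lymphocytes persisting in the pre-study biopsy. The share of BCG-treated patients is not given either: 2.1.5 says the population will be enriched for BCG failures, while 5.4 says no active enrichment will be attempted.

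These arguments limit the size of the point but do not remove it. The ceiling belongs to the scale and affects a descriptive table as much as a test. The 9.1.5 measures sit under biomarker activity, TILs have no stated unit, and nothing says how to read the infiltration result if H&E is flat while TILs or CD8 rise.

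**Conclusion.** The point holds for the 9.1.3 endpoint and is minor. That endpoint cannot register an increase in a tumor already containing lymphocytes, so it can show no change despite a real rise. Whether this matters a little or a lot turns on a baseline share the documents do not give. In the best case with 20 pairs, the endpoint moves from largely usable at 50% to 60% baseline-positive to nearly uninformative at 80% to 90%. These figures rest on an assumed two-sided alpha of 0.05 and no reversions. Fewer pairs or incomplete conversion lowers them. The endpoint is secondary and descriptive, and the safety objective is untouched.

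**What to change.** In 9.1.3, have the same pathologist also record, on the same H&E slides, the percentage of tumor area occupied by lymphocytes. This follows 9.1.4, which already pairs present/absent with an area. Analyze the within-patient change with the paired continuous method in 9.4; the non-parametric option there would suit a skewed percentage. Keep present/absent as a descriptive line. Add a sentence stating that the TIL and CD4/CD8 measures in 9.1.5 also serve the first secondary objective.

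The cost is a change of wording, one or two fields on the pathology form and a little more reading time. No extra tissue or procedure is needed.

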9.1.4 Residual tumor

This will be reported as whether there is any residual tumor in the surgical specimen (present /absent) as well as area of the surgical specimen comprised of residual tumor.

9.1.5 Biomarker activity

Immunological markers include CD4 and CD8 T cells and biomarker activity includes TILs, PD-1 and PD-L1 levels. These will be measured from the biopsy samples and surgical specimens.

9.1.6 Tumor Yield.

The amount of residual tumor available for analysis and the numbers of patients with assessable samples will be recorded.

9.1.7 Human Microbiome

The human microbiome profile by 16S ribosomal sequencing will be obtained from urine and feces. These data will then be used in an ad hoc correlation with our pathologic endpoint.

9.2 Sample Size Considerations

A pilot group of 20 patients will be assessed to confirm the safety of pre-surgical pembrolizumab and also allow for preliminary studies of drug efficacy and markers of tissue activity. With this sample size and the interim monitoring described below, we will stop the trial early 68% of the time if the underlying population TOX rate is 30%, but only 16% at the target of 15%, and 0.7% if it is 5%. If the trial TOX rate is 15% (3/20), the 95% posterior credible interval would be (5.4%, 36.3%) using a prior of beta(1, 1).

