9.3 Safety Interim Analyses

The safety analyses will monitor TOX as defined above using the methods of Thall et al[9]. If there is high probability that the underlying TOX rate is greater than 15%, the trial will be held

until all treated patients have completed 30 days post-surgery or gone off study prior to that time. The trial will then be stopped early if the risk of severe toxicity has been confirmed. Formally, denoting TOX probability by p_{TOX} and assuming this follows a beta (1, 1) prior distribution, the trial will be held if $\text{Prob}(p_{TOX} > 0.15 \mid \text{data}) > 0.95$. Monitoring will start once the 5th patient has been on trial for 4 weeks (at the end of the first week of cycle 2). After that, monitoring will continue monthly until the 20th patient has been followed for the full treatment period. A 6th patient will only be enrolled once there is sufficient evidence that fewer than 2 patients have TOX, i.e. ≥ 4 of the first 5 patients complete 30 days after surgery with no TOX. For the purposes of ongoing monthly trial monitoring, patients will be evaluable if they have been treated and then either have a TOX or have gone 4 weeks without TOX. Patients who are without TOX at 4 weeks, but who develop TOX later within the treatment interval will count as having a TOX at the next monthly evaluation. Stopping rules and operating characteristics were calculated in MultcLean 2.1.

Note, that since we expect enrollment of 1-2 patients per month, it is possible that monthly monitoring may allow a small overrun of patients, but this is expected to be only 1-2 additional patients at any given look.

If there are this many (or more) patients with TOX:	2	3	4	5	6
Stop the trial if there are this many (or fewer) patients who are evaluable for TOX:	5	9	13	17	20*

*Always stop with 20 patients, but if 6 or more patients have a TOX event, then pembrolizumab is unsafe for 'window of opportunity' use at this dose and schedule.

The operating characteristics of this design based on simulations are summarized in the following table. Note, since accrual will continue during monitoring, it's possible that these results underestimate the numbers of patients by 1-2 patients at the higher TOX rates.

True Prob(TOX)	Pr(stop)	Median # Pts (25%, 75%)
0.05	0.03	20 (20, 20)
0.10	0.11	20 (20, 20)
0.15	0.25	20 (16, 20)
0.20	0.43	20 (5, 20)
0.25	0.60	12 (5, 20)

0.30	0.75	7 (5, 19)
0.35	0.86	5 (5, 12)
0.40	0.93	5 (5, 8)

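### Section 9.2 gives early-stopping probabilities of 68%, 16% and 0.7%, but the monitoring rule in Section 9.3 gives about 75%, 25% and 3%

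*Combined protocol and SAP*

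**What the plan says.** Section 9.2 (Sample Size Considerations) presents its stopping probabilities as properties of the design that follows: "With this sample size and the interim monitoring described below", the trial would "stop the trial early 68% of the time if the underlying population TOX rate is 30%, but only 16% at the target of 15" per cent, "and 0.7% if it is 5" per cent.

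Section 9.3 (Safety Interim Analyses) describes that monitoring. The TOX probability is modelled "assuming this follows a beta (1, 1) prior distribution", and the trial is held when the posterior probability that the TOX rate exceeds 0.15 is greater than 0.95. "Monitoring will start once the 5th patient has been on trial for 4 weeks", and a sixth patient may enter only when at least four of the first five have reached 30 days after surgery without TOX. The printed boundary is 2 TOX in 5 or fewer evaluable patients, 3 in 9, 4 in 13, 5 in 17 and 6 in 20, with a note that the trial always ends at 20.

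The section continues: "The operating characteristics of this design based on simulations are summarized in the following table". That table gives Pr(stop) of 0.75, 0.25 and 0.03 at TOX rates of 30%, 15% and 5%.

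**The concern.** The two sections give different stopping probabilities for one design at the same true rates. The gaps are 7 points at 30%, 9 points at 15%, and about a factor of four at 5%. Rounding or simulation error cannot account for them.

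Safety is the primary objective, and these probabilities are how Section 9.2 describes the error rates of the safety design. A reader of that section alone would think a drug exactly at the 15% target has about a one in six chance of ending the trial early, when under Section 9.3 it is about one in four. The mismatch also raises the question of which rule was reviewed and approved, because figures like those in Section 9.2 come from boundaries that act differently at the first look.

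**Working it through.** **Inputs, all from Sections 9.2 and 9.3.** Maximum n = 20; prior beta(1,1); threshold 0.15; cutoff 0.95; first look at 5 patients; boundary 2/5, 3/9, 4/13, 5/17, 6/20. Reaching 20 patients is not counted as an early stop.

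**Step 1: the boundary follows from the prior and cutoff.** With a beta(1,1) prior and x TOX in n patients, Prob(pTOX > 0.15 | data) = P(Bin(n+1, 0.15) ≤ x). For 2 in 5 this is 0.37715 + 0.39933 + 0.17618 = 0.9527, which is above 0.95, so the trial is held. For 2 in 6 it is 0.9262, so it is not. Repeating this for every n from 5 to 20 gives exactly the printed boundary.

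**Step 2: early-stop probability under that boundary.** The TOX count never falls and the boundary is constant within each block of patients. Looking after every patient from 5 to 19 is therefore the same as checking for at least 2 TOX by patient 5, 3 by 9, 4 by 13, 5 by 17 and 6 by 19. At each checkpoint, convolve the surviving distribution with the binomial for the new patients and remove the mass at or above the boundary.

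| Checkpoint | Stop, p = 0.05 | Stop, p = 0.15 | Stop, p = 0.30 |
|---|---|---|---|
| 2 of 5 | 0.0226 | 0.1648 | 0.4718 |
| 3 of 9 | 0.0032 | 0.0482 | 0.1395 |
| 4 of 13 | 0.0008 | 0.0251 | 0.0805 |
| 5 of 17 | 0.0002 | 0.0150 | 0.0536 |
| 6 of 19 | 0.0000 | 0.0015 | 0.0078 |
| **Total** | **0.0268** | **0.2546** | **0.7532** |

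**Step 3: compare with both sections.**

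| True TOX rate | Exact | Section 9.3 | Section 9.2 |
|---|---|---|---|
| 0.05 | 0.027 | 0.03 | 0.007 |
| 0.10 | 0.113 | 0.11 | not given |
| 0.15 | 0.255 | 0.25 | 0.16 |
| 0.20 | 0.429 | 0.43 | not given |
| 0.25 | 0.605 | 0.60 | not given |
| 0.30 | 0.753 | 0.75 | 0.68 |
| 0.35 | 0.862 | 0.86 | not given |
| 0.40 | 0.931 | 0.93 | not given |

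All eight Section 9.3 values reproduce to within 0.005. Counting a boundary crossing at patient 20 as a stop gives 2.7%, 25.8% and 76.7% at 5%, 15% and 30%, further from Section 9.2.

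**Step 4: can a different look schedule give the Section 9.2 figures?** No, if the first look is kept. At p = 0.05 that look alone stops with probability 1 − 0.95⁵ − 5(0.05)(0.95⁴) = 1 − 0.7738 − 0.2036 = 0.0226, already above 0.007. At p = 0.15 it stops with probability 1 − 0.4437 − 0.3915 = 0.1648, which uses up the whole 16%. At p = 0.30 it stops with probability only 0.4718, so 68% needs later looks, and those would push the 15% figure above 16%. Dropping the first look does not help: starting at 6 patients gives 0.97%, 19.4% and 71.9% (at 5%, 15% and 30%), and starting at 10 gives 0.35%, 14.5% and 67.9%.

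**Step 5: what does give them?** A 0.96 cutoff with beta(1,1) needs 3 TOX through patient 8, 4 through 12, 5 through 16 and 6 after that. The early-stop probabilities are then 0.0069, 0.1592 and 0.6756, matching all three Section 9.2 figures. A 0.95 cutoff with a beta(0.5, 0.5) prior gives the same boundary. Under either, 2 TOX in the first 5 would not stop the trial.

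**The case against.** The best reply is that nothing operational depends on the Section 9.2 sentence. The prior, cutoff, boundary, gate before the sixth patient and Pr(stop) column in Section 9.3 all agree, and the correct probabilities appear one section later. Section 9.2 also supports n = 20 in other ways: a 95% credible interval of 5.4% to 36.3% for 3 of 20, which is correct, and a stated wish for preliminary efficacy and tissue data. The sample size would not change. At 30% the discrepancy runs in a reassuring direction, since the actual rule stops an unsafe regimen more often than Section 9.2 claims. At 5% the gap is only 2 percentage points.

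All of that stands, and it limits the consequence. It does not reconcile the two sections.

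A second reply is that the calculation treats each patient's TOX status as known in turn, while the protocol looks monthly, counts patients as evaluable at 4 weeks, lets TOX arrive later and expects some overrun. Realised probabilities could therefore differ from 75%, 25% and 3%. That is also fair, but it does not rescue Section 9.2. The gate before the sixth patient requires 30-day post-surgical follow-up of at least four TOX-free patients among the first five, so the 2.3% stopping probability at a 5% rate holds whatever the delay.

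Finally, the origin of the Section 9.2 figures is conjecture. Two specifications produce them and the documents name neither.

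**Conclusion.** The concern holds. The 68%, 16% and 0.7% in Section 9.2 are not properties of the rule in Section 9.3, which gives 75.3%, 25.5% and 2.7%. Section 9.2 understates the chance of stopping at the 15% target by about 9 points and at 30% by about 7 points. At 5% it gives roughly a quarter of the true value (0.7/2.7 = 0.26).

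The exact figures assume TOX is known patient by patient, with a look after each patient from the fifth. The agreement across all eight rates indicates that the Section 9.3 simulation is equivalent to this. Late TOX, the hold-then-confirm step and overrun are not modelled. This is an error in the stated operating characteristics. It leaves the monitoring boundary intact, provided Section 9.3 is the rule the sponsor intended.

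**What to change.** The sponsor should confirm which monitoring rule applies.

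- If it is the rule in Section 9.3, replace the three probabilities in Section 9.2 with that section's values: about 75% at a 30% TOX rate, 25% at 15% and 3% at 5%. State that they come from the Section 9.3 table under its simulation assumptions.
- If the rule behind the Section 9.2 figures was intended, the prior or cutoff, the boundary table, the gate before the sixth patient and the operating characteristics table must all be revised together.

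Either way, both sections should carry one set of figures. The first option costs one sentence and no change to sample size, boundary or analysis; the stated chance of stopping at the target rate becomes less favourable, 25% instead of 16%. The second changes the operative safety rule and would need a substantive amendment.

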5.3 Randomization or Treatment Allocation

Patients will be enrolled sequentially without randomization. According to a standardized, dose escalating, phase 2 safety design a total of 20 patients may be enrolled.

Initially 3 patients will be studied at 200 mg given at weeks 1 and 4 by IV infusion. These patients will be followed for safety assessments every 3 weeks during the treatment phase and at 30 and 90 days post-op visits during the follow-up phase. If < 2 patients in the initial cohort of 3 experience a grade >3 drug related adverse event then a subsequent cohort of 17 patients at 200 mg dose will be enrolled.

The following stopping rules will apply: if at any time ≥ 3 patients experience a drug related grade 4 adverse event including bowel perforation or any drug related grade 3 skin or gastrointestinal adverse event without clinical improvement within 2 weeks of study drug discontinuation and/or initiation of corticosteroid therapy to treat the adverse event; no additional patients will be enrolled. If any grade 3 or higher adverse event that is possibly, probably or definitely related to study drug, with the exception of any grade 3 or higher adverse events that is potentially treatable with steroids and improves to grade 1 or better within 2 weeks of steroid therapy initiation and/or study treatment discontinuation, the above stopping rule would apply. Also excluded will be grade 3 lipase elevation as this is common with this agent but is almost universally asymptomatic. Grade 4 lipase elevation will be criteria for stopping. If during monitoring, a patient is found to have disease progression within the treatment study period then this will be counted as a grade 4 toxicity event and the above stopping rule would apply. If there is a >12 week delay to surgery due disease progression, then this will be counted as a grade 4 toxicity event and the above stopping rule would apply. If a patient suffers a drug related toxicity which results in an inability to perform

radical cystectomy further study enrollment will be stopped. If there is a > 12 week delay to surgery due to a drug related toxicity in 2 or more patients, further enrollment will be stopped. Once patients have received a maximum of two doses of pembrolizumab, they will undergo surgery at approximately 6 - 8 weeks. An assessment of tumor response will not be made prior to radical cystectomy.

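### The early-stopping probabilities in section 9.2 (68%, 16%, 0.7%) do not follow from the section 9.3 monitoring rule, which gives 75%, 25% and 3%, as the 9.3 table itself prints

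*Combined protocol and SAP*

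**What the plan says.** Section 9.2 (Sample Size Considerations) introduces its figures with "With this sample size and the interim monitoring described below", so they are offered as properties of the section 9.3 rule with 20 patients. It then says that "we will stop the trial early 68% of the time if the underlying population TOX rate is 30" per cent, "but only 16% at the target of 15%, and 0.7% if it is 5" per cent.

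Section 9.3 (Safety Interim Analyses) defines that rule. The TOX probability has a beta(1,1) prior, and the trial is held when the posterior probability that it exceeds 0.15 is above 0.95. Monitoring starts with the 5th patient. The stopping table, whose second row is labelled "Stop the trial if there are this many (or fewer) patients who are evaluable for TOX", reads 2 TOX in 5, 3 in 9, 4 in 13, 5 in 17, and 6 in 20, where the trial ends in any case. After that: "The operating characteristics of this design based on simulations are summarized in the following table". At true TOX rates of 0.05, 0.15 and 0.30 that table prints stopping probabilities of 0.03, 0.25 and 0.75.

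**The concern.** Two adjacent sections give different stopping probabilities for one rule, so at least one set is wrong. Safety is the primary objective, and the quantitative case for the sample size in 9.2 consists of these three probabilities and one credible interval. A reader of 9.2 alone would think that a treatment at the 15% target is halted about one time in six; if 9.3 is right, it is one time in four. That reader would also think the monitoring weaker at 30% than it is, and false stopping at 5% negligible.

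**Working it through.** **Inputs**, all from 9.2 and 9.3: maximum 20 patients; beta(1,1) prior; threshold 0.15; cut-off 0.95; first look at 5 patients. Reaching 20 patients is not an early stop, so the looks are taken after patients 5 to 19.

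**Step 1: the boundary.** With x TOX in n patients the posterior is beta(1 + x, 1 + n − x). The posterior probability that the TOX rate exceeds 0.15, at each printed boundary point and with one more patient:

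| Boundary point | Posterior probability | One more patient, same x |
|---|---|---|
| 2 of 5 | 0.953 | 2 of 6: 0.926 |
| 3 of 9 | 0.95003 | 3 of 10: 0.931 |
| 4 of 13 | 0.953 | 4 of 14: 0.938 |
| 5 of 17 | 0.958 | 5 of 18: 0.946 |
| 6 of 20 | 0.971 | not applicable |

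Every printed point exceeds 0.95, and adding a patient takes it below. The printed boundary is therefore the stated rule.

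**Step 2: the 9.3 table.** An exact binomial recursion carries the TOX count forward one patient at a time and removes, at each look, the probability on or over the boundary:

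| True TOX rate | Exact | 9.3 prints |
|---|---|---|
| 0.05 | 0.027 | 0.03 |
| 0.10 | 0.113 | 0.11 |
| 0.15 | 0.255 | 0.25 |
| 0.20 | 0.429 | 0.43 |
| 0.25 | 0.605 | 0.60 |
| 0.30 | 0.753 | 0.75 |
| 0.35 | 0.862 | 0.86 |
| 0.40 | 0.931 | 0.93 |

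All eight rows agree to within rounding or simulation error.

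**Step 3: the 9.2 figures.**

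| True TOX rate | 9.2 states | Exact under 9.3 | Difference |
|---|---|---|---|
| 30% | 68% | 75.3% | 7.3 points |
| 15% | 16% | 25.5% | 9.5 points |
| 5% | 0.7% | 2.7% | 2.0 points (2.7 / 0.7 = 3.9 times) |

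**Step 4: a floor that needs no recursion.** The first look stops on 2 or more TOX in 5, with probability 1 − (1 − p)^5 − 5p(1 − p)^4:

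- p = 0.05: 1 − 0.7738 − 0.2036 = 0.0226
- p = 0.15: 1 − 0.4437 − 0.3915 = 0.1648
- p = 0.30: 1 − 0.1681 − 0.3602 = 0.4718 (rounded terms give 0.4717)

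At 5% the first look alone is three times the 0.7% stated for the whole trial. At 15% it already uses up the stated 16%, yet the later looks add 25.5 − 16.5 = 9.0 points.

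**Step 5: a possible origin.** A cut-off of 0.96 instead of 0.95 drops the 2-of-5 stop and moves the boundary to 3 of 8, 4 of 12 and 5 of 16. It gives 0.676, 0.159 and 0.0069, which round to 68%, 16% and 0.7%. A beta(0.5, 0.5) prior with cut-off 0.95 gives the same values. The 9.2 numbers thus look like those of a stricter boundary, but the documents do not say so and the conclusion does not depend on it.

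**Step 6: the rest of 9.2.** For 3 TOX in 20 the posterior is beta(4, 18), with 95% interval 5.4% to 36.3%, as stated. Only the three stopping probabilities are affected.

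**The case against.** **Hold is not stop.** Section 9.3 holds the trial first: "The trial will then be stopped early if the risk of severe toxicity has been confirmed". Could 9.2 be counting confirmed stops? No. Requiring the boundary still to be met after 1 or 2 overrun patients gives about 69–72%, 21–23% and 2.3–2.6%, still not the 9.2 figures. At the first look there is no overrun to dilute the result, because "A 6th patient will only be enrolled once there is sufficient evidence that fewer than 2 patients have TOX", so the Step 4 floor also applies to confirmed stops. What stands is that 75%, 25% and 3% are probabilities of reaching the boundary and should be described that way.

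**Looks are monthly.** Section 9.3 expects 1–2 patients a month, so looks can miss n = 9, 13 and 17. Looks at 5, 6, 8, 10, 12, 14, 16 and 18, for example, give 70.6%, 22.7% and 2.5%. This also stands: the 9.3 values assume looks that do not miss those points. It does not rescue 9.2.

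**Limited consequence.** The correct figures are already in the section 9.2 points to, the stopping table staff would follow is right, and at 30% TOX the error understates protection. All true, and it limits the weight of the point.

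**A stronger reading concerns section 5.3.** A reader might infer that both sets of figures are defective because they leave out the 5.3 stops, such as the one beginning "If a patient suffers a drug related toxicity which results in an inability to perform" a radical cystectomy, and that the real chance of halting is at least the 9.3 value. The documents do not support this as an error. Both sections index their figures to the TOX rate, section 2.1.1 says that further stopping rules are in 5.3, and the rules do not conflict. No rate is given for the 5.3 events, so the size of any addition would be whatever one assumed. Nor is "at least" established: with monthly looks and confirmation before stopping, the probability can fall below the printed value if 5.3 events are rare.

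**Conclusion.** The point holds for the three probabilities in 9.2 and no further. Under the rule that 9.2 cites, the probabilities of reaching the TOX boundary are 75%, 25% and 3%, not 68%, 16% and 0.7%. This rests on the prior, threshold, cut-off and first look as stated, independent patients with a constant TOX rate, and a look after each patient from 5 to 19. Monthly looks or confirmation of a hold lower the values somewhat, but none of the variants of the stated rule described above reaches the 9.2 set.

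This is a reporting error in the sample-size justification. A reader might infer that the monitoring rule or the sample size is unsound. It is not shown to be: the boundary matches the stated rule, the 9.3 table is correct and the credible interval reproduces. It should be fixed because 9.2 understates the false-stop probability at the target rate in support of the primary objective, and because the correction is simple.

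**What to change.** In 9.2, replace 68%, 16% and 0.7% with 75%, 25% and 3%. Describe them as the probability of reaching the TOX stopping boundary in 9.3 with a look after each patient from the 5th, since 9.3 confirms a hold before it stops the trial. A short note that the 5.3 stops apply in addition is optional; it should not claim that the combined probability is at least the printed one.

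The cost is a text amendment of three numbers and one clause. The values are already in the 9.3 table, so no simulation is needed, and no boundary, gate or sample size changes. The downside is presentational: the stated chance of stopping at the 15% target becomes less favourable, rising from 16% to 25%.
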